7.5.3.1 Potentially Clinically Significant Laboratory Values

The frequency of Grades 1 through 4 hematology, biochemistry and urinalysis values and Grades 1 through 4 change from baseline as defined in the Guidance for Industry titled

“**Toxicity Grading Scale for Healthy Adult and Adolescent Volunteers Enrolled in Preventive Vaccine Clinical Trials**” (Appendix D) will be provided by treatment group (ASP3772 (1 μ g, 2 μ g, 5 μ g) or PCV13) and stage. Subjects treated with PCV13 will be combined into one group by stage.

7.5.3.2 Liver Enzymes and Total Bilirubin

The percentage of subjects with the following potentially clinically significant elevations in liver tests will be summarized for Alkaline Phosphatase (ALP), Alanine Transaminase (ALT), Total Bilirubin, Aspartate Transaminase (AST) and their combination. These parameters will be measured from a central laboratory.

The subject’s highest value during the investigational period (day of vaccination and through Day 30) will be used.

- ALT > 3xULN, > 5xULN, > 10xULN, >20xULN
- AST > 3xULN, > 5xULN, > 10xULN, >20xULN
- ALT or AST > 3xULN, > 5xULN, > 10xULN, >20xULN
- ALP > 1.5xULN
- Total Bilirubin >2xULN
- (ALT or AST > 3xULN) and Total Bilirubin > 2xULN
- (ALT and/or AST > 3xULN) and ALP < 2xULN and Total Bilirubin > 2xULN

The last 2 criteria where 2 or more parameters are evaluated will be with the measurements on the same day or up to a maximum of 1 day apart.

The denominator for each criterion will be the number of subjects who have at least one value during the investigational period. The number and percentage of subjects meeting the criteria during the investigational period will be summarized by treatment group (ASP3772 (1 μ g, 2 μ g, 5 μ g) or PCV13) and stage.

7.5.4 Vital Signs

The baseline visit is the last measurement taken prior to vaccine administration.

Vital signs (body temperature, systolic blood pressure, diastolic blood pressure, respiratory rate and pulse rate) will be summarized using the mean, standard deviation, minimum, maximum and median. Additionally, a within-subject change will be calculated per visit and or timepoint as the post-baseline measurement minus the baseline measurement.

Tables for potentially clinically significant vital signs will be generated using the definitions shown in Appendix C: **Grading Signs of Systemic Reactogenicity**. Subjects who have a change in grade from baseline to post baseline during the first hour after immunization (Table C1) and have a numeric change that is consistent with Table C2 will be considered to have a clinically meaningful change vital sign.

Summaries will be provided by treatment group (ASP3772 (1 μ g, 2 μ g, 5 μ g) or PCV13) and stage using the maximum value obtained post immunization. Subjects treated with PCV13 will be combined into one group by stage.

Reactogenicity events defined in Section 6.2.1.3 will be summarized by treatment group (ASP3772 (1 µg, 2 µg, 5 µg) or PCV13) and stage. All subjects within a stage given PCV13 will be combined.

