- a. Screening will be completed up to 28 days prior to study immunization. Subjects will be assigned a subject number for use throughout the study at the screening visit via the Interactive Response Technology (IRT) system
- b. Informed consent must be obtained prior to the performance of any study-related procedure and before Randomization.
- c. Subjects will be randomized via the IRT at the dosing visit.
- d. Medical history will be collected at screening in order to assess Inclusion/Exclusion criteria and will be reconfirmed prior to study immunization.
- e. A physical examination will be performed at screening visit (days -28 thru -3), prior to study immunization (day 1) and day 30 visits.
- f. Perform tests for Hepatitis B surface antigen (HBsAg), hepatitis B core antibody (anti-HBc), hepatitis A virus antibodies (immunoglobulin M), HCV antibody (anti-HCV) confirmed by reflex testing (HCV-RNA) and HIV antigen/antibody (type 1 and/or type 2) at screening.
- g. Perform screening test for amphetamines, barbiturates, benzodiazepines, cannabinoids, cocaine and opiates at screening visit. Repeat urine drug screening before study immunization.
- h. Serum pregnancy test will be done at the screening visit. Urine pregnancy test will be done at study immunization (day 1) and day 30 visits. Not necessary for female subjects who are not of childbearing potential (e.g., post-menopausal [defined as at least 1 year without any menses] or documented surgically sterile) at screening and dosing visit.
- i. Body temperature, blood pressure and pulse rate will be assessed in a sitting position. At the dosing visit, body temperature, blood pressure, pulse rate and respiratory rate will be assessed predose and approximately 30 min and 1 hour postdose. Predose vital signs should be collected close to the vaccination and should not be more than 30 minutes prior to dose administration. Body temperature will be collected by the subject daily through day 7 following the study immunization.

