8 REVISION AND RATIONALE

Version 1 of the SAP has been updated to include planned interim analyses, provide greater details of treatment assignment blinding for study personnel, update the analysis of exploratory endpoints and to correct assorted typographical errors.

Version 2 of the SAP has been updated to

1. Increased screening for Stage 2 to be consistent with the protocol from -28 days to -40 days.
2. Added: “Subjects who are given PPSV23 without previous exposure to PCV13 will not be included in the immunogenicity summaries.” These are subjects in Stage 2, Group 3 who should have received PCV13 before receiving PPSV23.
3. **CCI** [REDACTED]
4. Changed the algorithm for setting the value for LLOQ for the calculation of fold change in response to feedback from the FDA. Values below the LLOQ will be set to $\frac{1}{2}$ LLOQ for calculation of geometric means and set to LLOQ for calculation of fold changes.
5. **CCI** [REDACTED]
6. **CCI** [REDACTED]
7. Added a CMH rank test to examine the difference between ASP3772 and PCV13 in the number of reactogenicity reactions. Added a CMH statistics with scores=modridit to compare the severity for each type of reaction between each dose of ASP3772 and PCV13 after assigning an increasing score to each severity.
8. Added details for determining systemic reactogenicity events during the 1st hour post vaccination.

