10.3 Appendix C: Grading Signs of Systemic Reactogenicity

Vital signs measurements will be monitored for reactogenicity through 1 hour postdose in all Stage 1 Group 1 and Stage 2 Group 2 subjects. Oral temperature will be recorded by the subjects daily through day 7 post immunization.

Table C1.

Vital Signs†	Mild (Grade 1)	Moderate (Grade 2)	Severe (Grade 3)	Potentially Life-threatening (Grade 4)
Fever (°C)‡ (°F)‡	38.0 – 38.4 100.4 – 101.1	38.5 – 38.9 101.2 – 102.0	39.0 – 40 102.1 – 104	> 40 > 104
Tachycardia (bpm)	101 – 115	116 – 130	> 130	ER visit or hospitalization for arrhythmia
Bradycardia (bpm)§	50 – 54	45 – 49	< 45	ER visit or hospitalization for arrhythmia
Hypertension (systolic) (mm Hg)	141 – 150	151 – 155	> 155	ER visit or hospitalization for malignant hypertension
Hypertension (diastolic) (mm Hg)	91 – 95	96 – 100	> 100	ER visit or hospitalization for malignant hypertension
Hypotension (systolic) (mm Hg)	85 – 89	80 – 84	< 80	ER visit or hospitalization for hypotensive shock
Respiratory Rate (breaths per min)	17 – 20	21 – 25	> 25	Intubation

bpm: beats per minute; ER: emergency room

† Subject should be at rest for all vital sign measurements.

‡ Oral temperature; no recent hot or cold beverages or smoking. Subjects will be provided with an oral thermometer to record temperature daily through day 7 postimmunization.

§ When resting heart rate is between 60 and 100 bpm. Use clinical judgment when characterizing bradycardia among some healthy subject populations, e.g., conditioned athletes.

Table C2.

	Absolute change to include in calculations
Fever (°C)‡	As in Table above (change in Grade)
Tachycardia (bpm)	As in Table above (change in Grade)
Bradycardia (bpm)§	>10 bpm
Hypertension (systolic) (mm Hg)	>20 mmHg
Hypertension (diastolic) (mm Hg)	>15 mmHg
Hypotension (systolic) (mm Hg)	As in Table above (change in Grade)
Respiratory Rate (breaths per min)	>4 breaths/min

Stage 1 Group 1 and Stage 2 Group 2 subjects will be asked to record the below systemic reactogenicity symptoms through day 7 following study immunization.

Table C3.

Systemic (General)	Mild (Grade 1)	Moderate (Grade 2)	Severe (Grade 3)	Potentially Life-threatening (Grade 4)
Nausea/ Vomiting	No interference with activity or 1 – 2 episodes/24 hours	Some interference with activity or > 2 episodes/24 hours	Prevents daily activity, requires outpatient IV hydration	ER visit or hospitalization for hypotensive shock

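### The first-hour vital-sign rule states no direction, so read literally it counts recoveries as clinically meaningful changes

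*SAP*

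**What the plan says.** The rule in SAP 7.5.4 has two conditions. The first concerns "Subjects who have a change in grade from baseline to post baseline during the first hour after immunization", graded by Table C1 in Appendix C. The second is that they "have a numeric change that is consistent with Table C2 will be considered to have a clinically meaningful change vital sign".

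Table C2 has one column, headed "Absolute change to include in calculations". Its entries carry no sign: >20 mmHg for systolic hypertension, >15 mmHg for diastolic hypertension, >10 bpm for bradycardia and >4 breaths/min for respiratory rate. Fever, tachycardia and systolic hypotension have no numeric entry. They refer back to Table C1 with "As in Table above (change in Grade", so a change in grade is enough by itself.

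Three more statements fix how the rule is applied:

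- Baseline (SAP 7.5.4): "The baseline visit is the last measurement taken prior to vaccine administration".
- Timing (SAP Section 2, Table 1 footnotes): "respiratory rate will be assessed predose and approximately 30 min and 1 hour postdose". Protocol 5.4.2 gives the same day 1 time points without distinguishing the stages.
- Value used (SAP 7.5.4, the paragraph after the rule): summaries are made "using the maximum value obtained post immunization".

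SAP Section 8 gives the reason for this material: "Added details for determining systemic reactogenicity events during the 1st hour post vaccination".

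**The concern.** A rule meant to pick out first-hour reactions should count subjects who get worse. This one counts subjects whose grade differs from baseline, in either direction. A subject with a raised pre-dose reading that settles would sit in the same cell as a subject whose pressure rose after vaccination.

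The SAP does state direction elsewhere. SAP 6.2.1.5 records an abnormal ECG as an adverse event only if it has worsened, and SAP 7.5.3 separates laboratory shifts to low from shifts to high. SAP 6.2.1.3, SAP 7.5.4, SAP Appendix C and Protocol Appendix 12.7 give no direction for change in vital signs.

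Vital signs are among the primary safety endpoints. What is at stake is whether the table's counts mean what its title says, and whether two programmers would produce the same table.

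**Working it through.** The documents give no expected event rate for this rule, so there is no planned figure to reproduce.

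**Step 1. The literal rule.** Let b be the last pre-dose value and m the maximum of the 30-minute and 1-hour values. A flag is raised when grade(m) ≠ grade(b) and |m − b| exceeds the Table C2 entry. Where Table C2 has no number, the grade condition stands alone. The systolic grades in Table C1 are 141–150 (Grade 1), 151–155 (Grade 2) and >155 (Grade 3). Tachycardia starts at 101 bpm. The readings below are invented to exercise the rule.

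| Sign | Pre-dose | 30 min, 1 h | m − b | Grade | Flagged, maximum | Flagged, either reading |
|---|---|---|---|---|---|---|
| Systolic, hypertension row | 162 | 138, 136 | −24 | 3 → 0 | yes | yes |
| Pulse, tachycardia row | 105 | 95, 94 | −10 | 1 → 0 | yes | yes |
| Systolic, hypertension row | 158 | 150, 130 | −8 | 3 → 1 | no | yes (130: −28, 3 → 0) |
| Systolic, hypertension row | 146 | 128, 124 | −18 | 1 → 0 | no | yes (124: −22, 1 → 0) |
| Systolic, hypertension row | 132 | 156, 150 | +24 | 0 → 3 | yes | yes |

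Only the last row is a worsening. Rows three and four show the limit: under the maximum, both post-dose readings must be far enough below baseline before a fall counts.

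**Step 2. Can a sign convention repair it?** SAP 7.5.4 defines within-subject change as post-baseline minus baseline. If Table C2 is read with that sign, the hypertension rows work. The bradycardia row does not: a pulse of 62 falling to 48 has change −14, which is not >10, so only a rise in pulse could qualify. If Table C2 is read as unsigned, bradycardia works (14 > 10) and falls count under hypertension. Direction has to be set row by row, and the SAP does not do so.

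**Step 3. The maximum and the falling signs.** Take a pulse of 62, then 44 and 60. The maximum is 60 (no grade, change −2), so the Grade 3 value of 44 is missed. Take a systolic of 120, then 82 and 118. The maximum is 118, so the Grade 2 hypotension value of 82 is missed. For bradycardia and hypotension the maximum is the wrong extreme.

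**Step 4. Size, by simulation.** Assumptions, not from the documents: true systolic mean 135, between-subject SD 15, within-subject SD 8, independent readings rounded to whole mmHg, no vaccine effect. A 4 mmHg fall means both post-dose means are 4 lower. There were 4,000,000 simulated subjects per scenario. Share = recoveries / (worsenings + recoveries).

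| Scenario | Worsening | Recovery | Share |
|---|---|---|---|
| Maximum, no shift | 4.16% | 0.54% | 0.54/4.70 = 11% |
| Maximum, 4 mmHg fall | 1.72% | 1.42% | 1.42/3.14 = 45% |
| Either reading, no shift | 4.16% | 3.99% | 3.99/8.15 = 49% |
| Either reading, 4 mmHg fall | 1.72% | 7.43% | 7.43/9.15 = 81% |

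Without rounding, the maximum-value shares are about 12% and 46%. For one Stage 2 dose group of 99, the maximum-value recoveries are 99 × 0.0054 = 0.5 and 99 × 0.0142 = 1.4 subjects. With either reading they are 99 × 0.0399 = 4.0 and 99 × 0.0743 = 7.4.

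**Step 5. Sensitivity, maximum value.** Varying the systolic mean/SD over 125/14, 132/15 and 138/16, and the within-subject SD over 6, 8 and 10, gives recovery shares of 6–17% with no pre-dose elevation and 45–77% with a 5 mmHg elevation. For diastolic pressure (mean 76 or 80, SD 9, within-subject SD 5, 6 or 7) the shares are 9–17% and 65–88%.

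**The case against.** The best defence is context. The tables are of potentially clinically significant values, they use the Appendix C definitions, and the rows are named for abnormalities. A post-dose systolic of 138 meets no hypertension grade, so listing it there is odd. The word absolute may mean raw units rather than unsigned. This makes it likely that worsening was intended, and nothing suggests the sponsor means to count recoveries. It does not settle the text, because the bradycardia row cannot be read as signed and three rows have no numeric condition at all.

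Three stronger readings are tempting, and the documents do not support them.

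- **That recoveries make up most of the flags.** The 49% and 81% apply only if either reading can trigger the flag. SAP 7.5.4 refers to the maximum value, which gives 11 to 12% and 45 to 46% under the same assumptions.
- **That pre-dose readings tend to be raised.** No source in the documents says so. Protocol 5.4.2 requires at least 5 minutes seated, and the Table C1 footnote requires rest. The higher shares depend on this assumption.
- **That the primary safety comparison is biased.** SAP 7.5.4 separately summarises signed change from baseline and the graded events of SAP 6.2.1.3, and neither uses this rule. No test is specified for this table. Subjects are randomized within cohort, so recoveries are expected in all arms.

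**Conclusion.** The rule is wrong as written: followed literally, it labels some improvements as clinically meaningful first-hour changes. That conclusion and the worked cases rest on the text alone.

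The size depends on assumed blood-pressure distributions and on how the maximum-value sentence is applied. Under the base assumptions, recoveries are roughly one systolic flag in nine with no shift and a little under half with a 4 mmHg fall. If either reading can trigger the flag, they are about half and four fifths. All of these are illustrative.

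The consequence is inflated counts, and a diluted contrast with PCV13, in one descriptive safety table. It is not directional bias between arms. The maximum-value sentence adds a separate error in the other direction, since transient falls can be missed under bradycardia and hypotension.

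**What to change.** In SAP 7.5.4, define the event as a worsening of at least one Table C1 grade from the last pre-dose value, with a change in the direction of the named sign that meets Table C2. The direction is a rise for hypertension, tachycardia, fever and respiratory rate, and a fall for bradycardia and hypotension.

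Retitle the Table C2 column to say that the change is in the direction of the named sign, and reword the three rows without a number to refer to a worsening in grade.

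Replace the single maximum with the maximum post-dose value for signs defined by a rise and the minimum for bradycardia and hypotension.

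No grade or change threshold is altered and no new data are needed. The cost is two sentences, a column heading and three table cells in the SAP, plus the matching table specification.

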5.4.2 Vital Signs

Vital signs (body temperature, blood pressure and pulse rate) will be measured at screening, the dosing visit (day 1) and at each subsequent visit (day 7 and day 30 [all groups]). On day 1, vital signs (body temperature, blood pressure, pulse rate and respiration rate) will be collected pre-dose and 30 min and 1 hour post-dose. Vital signs will be collected after the subject has been in seated position for at least 5 minutes. When vital signs are scheduled for the same time as blood sample or study vaccine administration, then vital signs will be taken first. Blood pressure should be obtained using the same cuff size and the same arm. Abnormal findings will be documented as clinical events through day 7 and AEs post day 7.

Subjects will be instructed to measure and record in the electronic diary their body temperature daily through day 7. Subjects will also be instructed to measure and record their body temperature in case of illness and contact the site if elevated.

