12.7 Grading of Signs of Systemic Reactogenicity

Vital signs measurements will be monitored for reactogenicity through 1 hour postdose in all Stage 1 Group 1 and Stage 2 Group 2 subjects. Oral temperature will be recorded by the subjects daily through day 7 postimmunization.

Vital Signs†	Mild (Grade 1)	Moderate (Grade 2)	Severe (Grade 3)	Potentially Life-threatening (Grade 4)
Fever (°C)‡	38.0 - 38.4	38.5 - 38.9	39.0 - 40	> 40
(°F)‡	100.4 - 101.1	101.2 - 102.0	102.1 - 104	> 104
Tachycardia (bpm)	101 – 115			ER visit or hospitalization for arrhythmia
Bradycardia (bpm)§	50 – 54	45 – 49	< 45	ER visit or hospitalization for arrhythmia
Hypertension (systolic) (mm Hg)	141 – 150	151 – 155	> 155	ER visit or hospitalization for malignant hypertension
Hypertension (diastolic) (mm Hg)	91 – 95	96 – 100	> 100	ER visit or hospitalization for malignant hypertension
Hypotension (systolic) (mm Hg)	85 – 89	80 – 84	< 80	ER visit or hospitalization for hypotensive shock
Respiratory Rate (breaths per min)	17 – 20	21 – 25	> 25	Intubation

bpm: beats per minute; ER: emergency room

02 Dec 2019 Astellas Page 90 of 111

[†] Subject should be at rest for all vital sign measurements.

[‡] Oral temperature; no recent hot or cold beverages or smoking. Subjects will be provided with a digital thermometer to record oral temperature daily though day 7 postimmunization.

[§] When resting heart rate is between 60 and 100 bpm. Use clinical judgment when characterizing bradycardia among some healthy subject populations, e.g., conditioned athletes.

Stage 1 Group 1 and Stage 2 Group 2 subjects will be asked to record the below systemic reactogenicity through day 7 following study immunization.

Systemic (General)	Mild (Grade 1)	Moderate (Grade 2)	Severe (Grade 3)	Potentially Life-threatening (Grade 4)
Nausea/ Vomiting	No interference with activity or 1 – 2 episodes/24 hours	Some interference with activity or > 2 episodes/24 hours	Prevents daily activity, requires outpatient IV hydration	ER visit or hospitalization for hypotensive shock
Diarrhea	2 – 3 loose stools or < 400 g/24 hours	4 – 5 stools or 400 – 800 g/24 hours	6 or more watery stools or > 800 g/24 hours or requires outpatient IV hydration	ER visit or hospitalization
Headache	No interference with activity	Repeated use of non- narcotic pain reliever > 24 hours or some interference with activity	Significant; any use of narcotic pain reliever or prevents daily activity	ER visit or hospitalization

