6.2.1.3 Vital Signs

Vital sign measurements will be taken for one hour post immunization to assess systemic reactions to the immunization. Each of these will be graded and reported according to the definitions contained in the table below.

Vital Signs	Mild (Grade 1)	Moderate (Grade 2)	Severe (Grade 3)	Potentially Life-threatening (Grade 4)
Fever (°C)‡ (°F)‡	38.0-38.4 100.4-101.1	38.5-38.9 101.2-102.0	39.0-40 102.1-104	>40 >104
Tachycardia (bpm)	101-115	116-130	>130	ER Visit or hospitalization for arrhythmia
Bradycardia (bpm)	50-54	45-49	<45	ER Visit or hospitalization for arrhythmia
Hypertension (systolic) (mm Hg)	141-150	151-155	>155	ER visit or hospitalization for malignant hypertension
Hypertension (diastolic) (mm Hg)	91-95	96-100	>100	ER visit or hospitalization for malignant hypertension
Hypotension (systolic) (mm Hg)	85-89	80-84	<10	ER visit or hospitalization for hypotensive shock
Respiratory Rate (breaths per min)	17-20	21-25	>25	Intubation

bpm: beats per minute; ER: emergency room

† Subject should be at rest for all vital sign measurements.

‡ Oral temperature; no recent hot or cold beverages or smoking.

§ When resting heart rate is between 60 and 100 bpm. Use clinical judgment when characterizing bradycardia among some healthy subject populations, e.g., conditioned athletes.

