7.5.2 Clinical Events

Clinical events capturing reactogenicity will be collected by the subject in the electronic daily diary. Specific local reactions requiring responses are pain, tenderness, redness/erythema, swelling, hardness, and induration at the immunization site. Systemic reactions are nausea, vomiting, diarrhea, headache, fever, tiredness (fatigue), myalgia/muscle pain, and arthralgia with grades 1-4 defined for each. Subjects in stage 1 will be asked to report joint pain/arthralgia through day 7 postimmunization during the day 7 visit. This addition was requested by the FDA after the electronic diary was being used at the sites. The ePRO device will be revised for Stage 2 so that subjects will be asked to report symptoms of arthralgia daily for 7 days post immunization. Additionally, elevated daily body temperature will be summarized by grade: grade 1 mild (100.4-101.1), grade 2 moderate (101.2 – 102.0), grade 3 severe (102.1 – 104) grade 4 potentially life threatening (>104).

Data will be summarized for each study day collected in the diary (day 1 thru day 7) by grade and overall. The number of subjects and percentage who experience each type of reaction will

be provided. The maximum grade for each type of reaction (number and percentage of subjects) will be provided.

At the Day 7 visit the investigator will assess each type of reactogenicity and based on the discussion with the subject will assess these as related or not. Those that are assessed as not related by the investigator will be excluded from a second table summarizing related reactogenicity events. The maximum grade for each type of related reaction (number and percentage of subjects) will be provided. In the event there are none judged as not related, this summary will not be produced.

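### SAP 7.5.4 summarizes potentially clinically significant vital signs by the maximum post-dose value, which read literally under-counts hypotension and bradycardia; separately, the 6.2.1.3 table gives Grade 3 hypotension as <10

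*SAP*

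**What the plan says.** Three statements in SAP 7.5.4 (Vital Signs) bear on this.

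- **Event rule.** The table of potentially clinically significant vital signs uses the Appendix C definitions. The rule starts from "Subjects who have a change in grade from baseline to post baseline during the first hour after immunization (Table C1" and also requires a numeric change consistent with Table C2. Table C2, headed "Absolute change to include in calculations", asks for a fall of more than 10 bpm for bradycardia. For systolic hypotension it asks only for the change in grade.
- **Summary rule.** The next paragraph says the summaries are given by treatment group "and stage using the maximum value obtained post immunization".
- **A second output.** The section ends with a separate summary: "Reactogenicity events defined in Section 6.2.1.3 will be summarized by treatment group". SAP 6.2.1.3 introduces its own grading table with "Each of these will be graded and reported according to the definitions contained in the table below".

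Table C1 grades two signs downward: systolic hypotension (85-89, 80-84, <80 mmHg) and bradycardia (50-54, 45-49, <45 bpm). Protocol Appendix 12.7 has the same cut-offs for both. The SAP 6.2.1.3 table agrees except in one cell, where Grade 3 systolic hypotension is <10.

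Protocol 5.4.2 sets two post-dose readings on day 1; vital signs "will be collected pre-dose and 30 min and 1 hour post-dose". Protocol Appendix 12.7 gives the purpose: "Vital signs measurements will be monitored for reactogenicity through 1 hour postdose".

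**The concern.** There are two separate defects, in two different outputs.

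**Maximum value.** For a sign graded upward (fever, tachycardia, hypertension, respiratory rate) the maximum is the worst reading. For hypotension and bradycardia it is the best one. A literal program would therefore grade these two signs only when every post-dose reading is below the threshold. The event rule in the preceding paragraph needs only a grade change during the first hour. The two rules give different counts from the same data, and the SAP does not rank them. The summary sentence is also not limited to the first hour, so it is unclear whether Day 7 and Day 30 readings enter the maximum.

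**The <10 cell.** With Grade 2 at 80-84 and Grade 3 at <10, systolic values from 10 to 79 mmHg have no numeric grade in the reactogenicity-event summary.

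Vital signs are listed among the primary safety endpoints in both stages (Protocol 2.3), and this is a first-in-human vaccine study. Both literal rules err in one direction only, toward fewer low-pressure and low-pulse events, and two programmers could produce different tables from the same text.

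**Working it through.** The plan gives no figure to reproduce, so the check has three parts: grading example readings, a logical bound, and an illustrative size.

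**1. Example readings, graded by Table C1 and Table C2**

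| Sign | Predose | 30 min, 1 h | By maximum | By lowest value |
|---|---|---|---|---|
| Systolic | not low | 78, 95 | no grade | Grade 3 |
| Systolic | not low | 82, 88 | Grade 1 | Grade 2 |
| Pulse | 62 | 44, 58 | no grade; fall 62 - 58 = 4 bpm | Grade 3; fall 62 - 44 = 18 bpm |
| Pulse | 62 | 48, 52 | Grade 1, but fall 62 - 52 = 10 bpm, not above 10, so not counted | Grade 2; fall 62 - 48 = 14 bpm, counted |

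With the 6.2.1.3 cell at <10, a systolic value of 78 has no numeric grade. A value of 82 is Grade 2 in every copy. The unassigned range is 10 to 79, that is 79 - 10 + 1 = 70 integer values.

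**2. Bound.** For a threshold c, the maximum is below c only if both readings are. The lowest value is below c if either is. The count by maximum therefore cannot exceed the count by lowest value, and it is smaller whenever one reading recovers.

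**3. Illustrative size.** The documents give no means, SDs or correlations, so all of these are assumed. Baseline, 30-minute and 60-minute values are exchangeable normal, rounded to integers, with no vaccine effect and 2,000,000 simulated subjects per setting. A hypotension event is a Table C1 grade above the baseline grade. A bradycardia event also needs a fall of more than 10 bpm. Entries are expected subjects per 99 (one Stage 2 dose arm): lowest value versus maximum, with the share captured in brackets.

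| Assumed mean, SD | Correlation 0.5 | 0.7 | 0.9 |
|---|---|---|---|
| Systolic 120, 12 | 0.96 vs 0.044 (5%) | 0.84 vs 0.081 (10%) | 0.56 vs 0.105 (19%) |
| Systolic 125, 15 | 1.54 vs 0.083 (5%) | 1.31 vs 0.132 (10%) | 0.90 vs 0.177 (20%) |
| Systolic 130, 18 | 2.07 vs 0.130 (6%) | 1.75 vs 0.207 (12%) | 1.18 vs 0.249 (21%) |
| Pulse 68, 10 | 7.01 vs 0.606 (9%) | 3.88 vs 0.344 (9%) | 0.40 vs 0.017 (4%) |
| Pulse 72, 10 | 3.81 vs 0.244 (6%) | 2.13 vs 0.153 (7%) | 0.21 vs 0.008 (4%) |
| Pulse 70, 11 | 7.05 vs 0.621 (9%) | 4.18 vs 0.387 (9%) | 0.60 vs 0.032 (5%) |

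The Table C1 footnote limits bradycardia to a resting rate of 60-100 bpm. Applying it at baseline lowers the top bradycardia figure from about 7.1 to about 6.2 per 99 and leaves the captured share at roughly 4-10%.

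A second model was also run: subject means with SD 15 mmHg around 125 and SD 10 bpm around 70, plus within-subject SD of 4 to 10. With two readings the maximum captured 13-22% of hypotension and 7-13% of bradycardia. With four readings (adding Day 7 and Day 30) it captured about 1-5% and 0.4-1.2%.

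**Reach of the <10 cell.** The chance that one reading is below 80 is P(Z < (80 - mean)/SD). This is 0.04% for mean 120 and SD 12, 0.13% for 125 and 15, and 0.27% for 130 and 18. Multiplying by 2 readings and 99 subjects gives about 0.08, 0.27 and 0.54 subjects as upper bounds.

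**The case against.** The strongest reply is that the event rule already decides who is counted, and that a programmer working with grades would read maximum value as maximum grade. On that reading nothing is lost. The table specifications, which are not part of these documents, may settle it. This stands as a possible reading, and the conclusion is limited to the literal one. But the SAP does not state that reading, and elsewhere it chooses its words more carefully. For diary reactions SAP 7.5.2 says "The maximum grade for each type of reaction (number and percentage of subjects) will be provided", and SAP 7.5.3 uses the worst finding for laboratory shifts. Only 7.5.4 applies a raw maximum to signs graded in both directions.

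It is also true that the information survives elsewhere. The descriptive summaries include the minimum and per-timepoint changes, all vital signs are listed, and abnormal findings are still recorded as clinical events or adverse events. The closing reactogenicity summary is not tied to the maximum. No hypothesis test, sample size or stated escalation criterion depends on this table. That limits the consequence to two categorical tables.

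The magnitudes rest on assumed inputs, and the bradycardia range is wide (0.2 to 7.1 per 99), mainly because of the assumed correlation. This is fair, and the figures are illustrative only. In a Stage 1 dose arm of 30, hypotension by lowest value would be about 0.6 x 30/99 = 0.2 to 2.1 x 30/99 = 0.6 subjects.

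Finally, <10 is probably a typing error, and an error in reading the PDF cannot be excluded without the source page. It is an easy slip to notice, but SAP 7.5.4 does send a summary to that table.

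**Conclusion.** The point holds. Read literally, the SAP 7.5.4 maximum-value sentence under-counts hypotension and bradycardia in the potentially clinically significant table, and it conflicts with the first-hour event rule before it. Under the main assumed settings with two first-hour readings, it would show 0.04-0.25 instead of 0.6-2.1 hypotension subjects per 99, and 0.01-0.62 instead of 0.2-7.1 bradycardia subjects per 99. The size depends on the assumed means, SDs and correlations. Under the literal rule the direction does not; if the event rule or the maximum grade is what is meant, the loss is zero and only the wording is at fault.

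The <10 cell is a separate inconsistency. It affects Grade 3 systolic hypotension in the 6.2.1.3 reactogenicity summary only, at most about 0.1-0.5 subject per 99 under the same blood pressure assumptions. Hypotension Grades 1-2 and all bradycardia grades agree across the three copies. Both defects should be corrected; neither undermines the design.

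**What to change.** - In SAP 7.5.4, replace the maximum value with the worst post-immunization value in the graded direction: lowest for hypotension and bradycardia, highest for the other signs. The maximum grade per sign would serve equally well.
- State that the first-hour grade change together with the Table C2 change defines the event, and say whether readings after the first hour enter this table.
- Check the 6.2.1.3 cell against the source page and reconcile that table with Table C1 and Protocol Appendix 12.7, so that one set of cut-offs is programmed. Replacing the 6.2.1.3 table with a reference to the reconciled table would prevent a recurrence.

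The cost is two short SAP wording edits. No new data, visits or analyses are needed.
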